4.2.4. Elimination from unsolicited and solicited safety set

4.2.4.1. Excluded subjects

4.2.4.1.1. Unsolicited safety set

Code 1030 (Study vaccine not administered at all), code 800 (fraudulent data) and code 900 (invalid informed consent) and code 1150 (no post-vaccination safety data) will be used for identifying subjects eliminated from the unsolicited safety set.

4.2.4.1.2. Solicited safety set

Code 1030 (Study vaccine not administered at all), code 800 (fraudulent data) and code 900 (invalid informed consent) and code 1160 (no post-vaccination solicited safety data) will be used for identifying subjects eliminated from the solicited safety set.

5. STATISTICAL ANALYSES

The standard data derivation rules and stat methods are described in section 10.1 while the study specific data derivation rules and stat methods are described in section 9.

CONFIDENTIAL209544 (RSV MAT-004)
Statistical Analysis Plan Amendment 3**5.1. Demography****5.1.1. Analysis of demographics/baseline characteristics planned in the protocol**

These analyses will be performed on the Exposed set and on the Per protocol set for immunogenicity.

For all maternal subjects, demographic characteristics (e.g., age at vaccination (18 - <35; ≥ 35 years), gestational age at vaccination ($28^{0/7}$ - $31^{0/7}$, $31^{1/7}$ - $33^{6/7}$ weeks), geographic ancestry will be summarized by group using descriptive statistics. The interval in days between maternal vaccination and delivery will be calculated and summarized by group using descriptive statistics.

For their infants, demographic characteristics (e.g., gestational age at time of delivery (> 37 weeks; ≤ 37 weeks), sex, weight, length, head circumference, geographic ancestry, apgar score), and lifestyle characteristics (e.g., living environment, household composition, breastfeeding, passive smoking and extent of contact with children less than 6 years of age) will be summarised by group, and for each immunogenicity sub-cohort within each group, using descriptive statistics.

- Frequency tables will be generated for categorical variable such as geographic ancestry.
- Mean, median, standard deviation and range will be provided for continuous data such as age.

5.1.2. Additional considerations

Demographic characteristics will also be summarized on Enrolled Set for web public disclosure.

Subgroup analysis for demographic characteristics by age category at vaccination (18 - <35; ≥ 35 years) for maternal subjects and by gestational age at birth (> 37 weeks or ≤ 37 weeks) for infant subjects will also be performed on Enrolled Set, ES or PPS.

Subject disposition will be summarized by group using descriptive statistics:

- Number of maternal subjects screened, randomised, vaccinated and withdrawn including withdrawal reasons in each group and overall will be tabulated.
- Number of infants enrolled and withdrawn including withdrawal reasons will be tabulated by group, by sub-cohort within each group and overall.

Vital signs will be summarized by group using descriptive statistics at all timepoint(s) the information is collected on Exposed Set and Per-protocol Set. The parameters include but may not be limited to systolic blood pressure, diastolic blood pressure, temperature, heart rate, respiratory rate, height, weight and body mass index.

CONFIDENTIAL209544 (RSV MAT-004)
Statistical Analysis Plan Amendment 3

Summary of important protocol deviations leading to elimination will be tabulated by group. An individual listing will also be provided.

Summary of medical history will be performed on Exposed Set by Medical Dictionary for Regulatory Activities (MedDRA) and preferred term if available.

Additional analyses by country and/or by site may be performed if deemed necessary.

5.2. Immunogenicity

5.2.1. Analysis of immunogenicity planned in the protocol

The primary analysis will be based on the Per Protocol set for analysis of immunogenicity. If, in any study group and at any timepoint, the percentage of vaccinated subjects with serological results excluded from the Per Protocol set for analysis of immunogenicity is 5% or more, a second analysis based on the Full Analysis Set will be performed to complement the Per Protocol analysis.

	Primary Immunogenicity Endpoints	Statistical Analysis Methods
Maternal subjects	
 • RSVPreF3 IgG-specific antibody concentration, and • Neutralizing antibody titers against RSV-A 
Measured on blood samples collected from vaccinated maternal subjects at Day 1 before vaccination (Visit 1), Day 31 (Visit 3), and at Delivery (Visit 5).
	
For each assay, at each timepoint and by study group and age category (18 - <35 years; ≥ 35 - years; overall):
 
 • Antibody titres/concentrations will be displayed using reverse cumulative curves. • Geometric Mean Titers (GMTs)/ Geometric Mean Concentrations(GMCs) will be tabulated with 95% CI and represented graphically. • Individual post-vaccination versus pre-vaccination results will be plotted using scatter plots. Results of the control group will be used as a reference. • Geometric mean of ratios of antibody titres/concentrations at each post-vaccination timepoint over pre-vaccination will be tabulated with 95% CI. • The distribution of antibody titres/concentration will be tabulated • Distribution of the fold increase of the antibody titres/concentrations (post- versus pre-vaccination) will be tabulated by pre-specified pre-vaccination titre category. 
Relationship between maternal RSVPreF3 IgG-specific antibody concentration and RSV-A neutralizing antibody at baseline, at day 31 and at delivery will be explored using scatter plots of individual values. Between group evaluation of vaccine formulations in terms of RSVPreF3 IgG-specific antibody concentrations and Neutralizing antibody titers against RSV-A will be performed at Day31 and at Delivery using a mixed effect model on the logarithm₁₀ transformation of the concentrations/titers, and including the pre-vaccination logarithm₁₀ transformation of the concentrations/titers, the vaccine groups, gestational age at vaccination, age category at vaccination, center and the interval between vaccination and delivery as covariates if needed.

CONFIDENTIAL209544 (RSV MAT-004)
Statistical Analysis Plan Amendment 3

Primary Immunogenicity Endpoints		Statistical Analysis Methods
Cord blood/ placental transfer	
 • RSVPreF3 IgG-specific antibody concentration, and • Neutralizing antibody titers against RSV-A 	
For each assay, the following analysis will be performed by study group
 
 • Antibody titres/concentrations will be displayed using reverse cumulative curves. • Geometric Mean Titers (GMTs)/ Geometric Mean Concentrations (GMCs) will be tabulated with 95% CI and represented graphically. • The distribution of RSV-A and RSVPreF3 IgG-specific antibody titres/concentration from cord blood will be tabulated • For each assay, relationship between maternal antibody titers/concentrations and infant antibody titers/concentrations at the time of delivery will be evaluated graphically using scatter plots of individual results.
	
 • The ratio between cord blood and maternal RSVPreF3 IgG-specific antibody concentrations 
All 3 endpoints measured on blood samples collected from maternal subjects at delivery and either cord blood, or (if cord blood cannot be collected) infant blood samples collected within 3 days after birth
	
 • Geometric mean of placental transfer will be tabulated with 95% CI by study group. • Percentage of infants with placental transfer ≥ 1 will be tabulated with exact 95 % CI by study group. 
Between group evaluation on vaccine formulations in terms of RSVPreF3 IgG-specific antibody concentrations / neutralizing antibody titers will be performed on cord blood at Delivery using a mixed effect model on the logarithm₁₀ transformation of the concentrations/titers, including the pre-vaccination logarithm₁₀ transformation of the concentrations/titers from maternal subjects, the vaccine groups, gestational age at vaccination, gestational age at birth (> 37 weeks; \leq 37 weeks), age category at vaccination, center and the interval between vaccination and delivery as covariates if appropriate.
 
In addition, if cord blood samples are missing in 20% or more of infants in a single study group, and if the data permit: RSV antibody concentrations/titers and persistence of RSV antibody concentrations/titers in infants through time will be evaluated separately in infants with cord blood samples and in infants from whom, instead, a blood sample was obtained within 3 days after birth.
 
The relationship between RSVPreF3 IgG-specific antibody concentration and RSV-A neutralizing antibody at delivery will be explored using scatter plots of individual values.

CONFIDENTIAL209544 (RSV MAT-004)
Statistical Analysis Plan Amendment 3

	Secondary Immunogenicity Endpoints	Statistical Analysis Methods
Maternal subjects	
 • RSVPreF3 IgG-specific antibody concentration, and • Neutralizing antibody titers against RSV-A and • Neutralizing antibody titers against RSV B 
For RSV-A: Measured on the blood sample collected Day 43 post-delivery (Visit 6).
 
 • For RSV-B: Measured on blood samples collected from vaccinated maternal subjects at Day 1 before vaccination (Visit 1), Day 31 (Visit 3),, at Delivery (Visit 5) and at Day 43 post delivery (Visit 6). 	
For each assay, at each timepoint and by study group and age category (18 - <35 years ; ≥ 35 - years; overall):
 
 • Antibody titres/concentrations will be displayed using reverse cumulative curves. • GMTs/ GMCs will be tabulated with 95% CI and represented graphically. • Individual post-vaccination versus pre-vaccination results will be plotted using scatter plots. Results of the control group will be used as a reference. • Geometric mean of ratios of antibody titres/concentrations at each post-vaccination timepoint over pre-vaccination will be tabulated with 95% CI. • The distribution of antibody titres/concentration will be tabulated • Distribution of the fold increase of the antibody titres/concentrations (post- versus pre-vaccination) will be tabulated by pre-specified pre-vaccination titre category. 
Relationship between maternal RSVPreF3 IgG-specific antibody concentration and RSV-A neutralizing antibody, between RSV-A neutralizing antibody and RSV-B neutralizing antibody, and between RSV-B neutralizing antibody and RSVPreF3 IgG-specific antibody concentration at baseline, at day 31, at delivery and at day 43 post-delivery will be explored using scatter plots of individual values.
 
In addition, between group evaluation of vaccine formulations in terms of RSVPreF3 IgG-specific antibody concentrations and Neutralizing antibody titers against RSV-A and RSV-B will be performed at Day31, at Delivery and at Day 43 post-delivery using a mixed effect model on the logarithm₁₀ transformation of the concentrations/titers, and including the pre-vaccination logarithm₁₀ transformation of the concentrations/titers, the vaccine groups, gestational age at vaccination, and the interval between vaccination and delivery if available as covariates if needed.

Infant subjects	
 • RSVPreF3 IgG-specific antibody concentration • Neutralising antibody titres against RSV-A • Neutralising antibody titres against RSV-B 
For all 3 RSV-specific antibody assessments: measured in a subcohort of infants at Day 43 after birth (sub-cohort V2-NB), in a subcohort of infants at Day 121 (sub-cohort V3-NB) after birth and in a subcohort of infants at D181 after birth (sub-cohort V4-NB). Each infant will be randomly assigned to 1 of
	
For each assay, at each timepoint and by study group
 
 • Antibody titres/concentrations will be displayed using reverse cumulative curves. • GMTs/ GMCs will be tabulated with 95% CI and represented graphically. 
In addition, analyses will include exploratory evaluation of the persistence of RSV specific antibodies in infants through time, and half-life analysis modelling of logarithm transformed RSV antibody concentrations/titers over time.
 
Between group evaluation on vaccine formulations in terms of RSVPreF3 IgG-specific antibody concentrations / neutralizing antibody titers will be performed on cord blood at Delivery, and on blood samples collected at 6 weeks, 4 months and 6 months post-birth using a mixed effect model on the logarithm₁₀ transformation of the concentrations/titers,

CONFIDENTIAL209544 (RSV MAT-004)
Statistical Analysis Plan Amendment 3

	Secondary Immunogenicity Endpoints	Statistical Analysis Methods
	
these 3 cohorts at the time of maternal randomization to intervention
 
For neutralizing antibody titers against RSV-B only: measured on the cord blood sample collected at delivery, or on a blood sample collected from the infant within 3 days after birth (if no cord blood sample can be obtained). (Note: RSV-A neutralizing antibody at birth is a primary immunogenicity objective).
	
including the pre-vaccination logarithm₁₀ transformation of the concentrations/titers from maternal subjects, the vaccine groups, gestational age at vaccination, gestational age at birth (> 37 weeks ; ≤ 37 weeks), and the interval between vaccination and delivery as covariates if appropriate and needed.
 
In addition, if cord blood samples are missing in 20% or more of infants in a single study group, and if the data permit: RSV antibody concentrations/titers and persistence of RSV antibody concentrations/titers in infants through time will be evaluated separately in infants with cord blood samples and in infants from whom, instead, a blood sample was obtained within 3 days after birth.
 
The relationship between RSVPreF3 IgG-specific antibody concentration and RSV-A neutralizing antibody, between RSV-A neutralizing antibody and RSV-B neutralizing antibody, and between RSV-B neutralizing antibody and RSVPreF3 IgG-specific antibody concentration at delivery will be explored using scatter plots of individual values.

5.2.2. Additional considerations

Before unblinding occurs, the immunogenicity analysis will only be performed on Exposed Set. At the time of final analysis, the immunogenicity analysis will be performed on PPS.

5.2.2.1. Distribution analysis

RSV-A neutralizing antibody titers and RSV-B neutralizing antibody titers:

- Number and percentage of subjects with titers <128, ≥128, ≥256, ≥512, ≥1024, ≥2048, ≥4096, ≥8192 and ≥16384 will be tabulated.
- For distribution of fold increase, number and percentage of subjects with a fold increase above or equal to 2, 4, 6, 8, 10 and 12 by pre-vaccination category (< 128, ≥128 and <256, ≥ 256 and <512, ≥ 512 and <1024, ≥1024 and <2048, ≥ 2048 and <4096, ≥ 4096 and <8192, ≥8192 and <16384) will be tabulated.

RSVPreF3 IgG-specific antibody concentrations:

- Number and percentage of subjects with concentrations <2048, ≥2048, ≥4096, ≥8192, ≥16384, ≥32768, ≥65536, ≥131072 will be tabulated.
- For distribution of fold increase, number and percentage of subjects with a fold increase above or equal to 4, 6, 8, 10, 12, 14 and 16 by pre-vaccination category (< 2048, ≥2048 and <4096, ≥ 4096 and <8192, ≥ 8192 and <16384, ≥16384 and <32768, ≥ 32768 and <65536, ≥ 65536 and <131072, ≥131072) will be tabulated.

The thresholds for distribution tables of titres and concentrations and fold increase may be further adjusted at analysis as needed.

CONFIDENTIAL209544 (RSV MAT-004)
Statistical Analysis Plan Amendment 3

In addition, to assess the effect of the interval between vaccination and delivery on the antibody transfer, geometric mean of RSV-A neutralizing antibody titers, RSVPreF3 IgG-specific antibody concentrations and RSV-B neutralizing antibody titers from cord blood (or blood drawn from infants within 3 days after birth) will be tabulated with different categories of time (in weeks) from vaccination to delivery. This analysis will be performed for infants born at gestational age <37 weeks and those born at gestational age \geq 37 weeks. Associated scatter plots may also be provided as needed.

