Statistical Analysis Plan Amendment 3

Primary Immunogenicity objectives	Primary Immunogenicity endpoints
To evaluate the immunogenicity of a single IM dose of study vaccine in maternal subjects at Day 31 and at Delivery.	RSVPreF3 IgG-specific antibody concentration, and Neutralizing antibody titers against RSV-A Measured on blood samples collected from vaccinated maternal subjects at Day 1 before vaccination (Visit 1), Day 31 (Visit 3), and at Delivery (Visit 5).
To evaluate RSV-specific antibody levels in infants born to maternal subjects who were vaccinated with a single IM dose of study vaccine at birth j	RSVPreF3 IgG-specific antibody concentration, and Neutralizing antibody titers against RSV-A. Measured on the cord blood sample collected at delivery, or on a blood sample collected from the infant within 3 days after birth (if no cord blood sample can be obtained).
To evaluate the transfer of RSV-specific antibodies from maternal subjects vaccinated with a single IM dose of study vaccine to their infants at the time of delivery.	The ratio between cord blood* and maternal RSVPreF3 IgG-specific antibody concentrations *or an infant blood sample collected within 3 days after birth (if no cord blood sample can be obtained).
Secondary Safety objectives	Secondary Safety endpoints
To evaluate the safety of a single IM dose of study vaccine in maternal subjects, up to 6 months after delivery	From Day 1 (Visit 1) through 6 months after delivery (Visit 8), occurrences of SAEs, MAEs, and AEs leading to study withdrawal.
To evaluate the safety of the vaccine in infants born to maternal subjects who were vaccinated with a single IM dose of study vaccine, up to 1 year of age	From birth through 6 months (Visit 4-NB) after birth, occurrences of SAEs, AEs leading to study withdrawal, and MAEs From birth through 1 year (Visit 5-NB) after birth, occurrences of SAEs, AEs leading to study withdrawal, and MAEs.
To estimate the incidence of RSV-associated, medically attended RTIs (MA-RTIs) in maternal subjects vaccinated with a single IM dose of study vaccine, from vaccination up to 6 months post-delivery (Visit 8).	Occurrence of RSV-associated MA-RTIs (RSV-MA-RTIs) up to 6 months post-delivery (Visit 8)

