8. CHANGES FROM PLANNED ANALYSES

To take a more practical approach, subgroup analysis of safety by age category at vaccination (18 - <35; \geq 35 years) in maternal subjects will include summaries of pregnancy outcomes, pregnancy related AESIs, SAEs, MAEs and MA-RTIs.

Subgroup analysis of safety by gestational age at birth (> 37 weeks or \leq 37 weeks) in infant subjects will include summaries of neonatal AESIs, MAEs, SAEs, and occurrence of RSV-associated RTIs, LRTIs, severe LRTIs, very severe LRTIs and RSV-associated hospitalizations.

Subgroup analysis on other safety summaries will be performed if deemed necessary.

Subgroup analysis of immunogenicity by age category at vaccination (18 - <35; \geq 35 years) for maternal subjects and by gestational age at birth ((> 37 weeks or \leq 37 weeks) for infants will include analysis of GMT(C) and GMR calculation at each time point and geometric mean of placental transfer.

Subgroup analysis on other immunogenicity analysis will be performed if deemed necessary.

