9.1.2. Immunogenicity

For a given subject and given immunogenicity measurement, missing or non-evaluable measurements will not be replaced. Therefore, an analysis will exclude subjects with missing or non-evaluable measurements.

- For the within-group assessment, the descriptive analysis performed for each assay at each timepoint will exclude subjects with a missing or non-evaluable measurement.
- For the between group assessments, statistical model will be fitted based on the subjects having a result at both the baseline and the considered timepoint.

The GMT/GMC and its 95% CI will be obtained by exponentiating the mean and its 95% CI of the log-transformed titres/concentrations. All CI computed will be two-sided 95% CI.

Placental transfer is defined as the ratio of RSVPreF3 IgG-specific antibody concentrations between cord blood (or blood sample from infants collected within 3 days after birth if cord blood is not available) and maternal blood sample at delivery (or within 3 days after delivery if blood sample is not collected during delivery).

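### SAP 5.2.2.1 sets out to assess how the vaccination-to-delivery interval affects antibody transfer but tabulates only cord-blood levels, so the table alone cannot tell a change in transfer from a change in maternal level

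*SAP*

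**What the plan says.** The current SAP (Amendment 3), section 5.2.2.1, gives the purpose of this analysis and the first of its outcomes as "to assess the effect of the interval between vaccination and delivery on the antibody transfer, geometric mean of RSV-A neutralizing antibody titers". The other quantities it reports are geometric means of RSVPreF3 IgG concentration and "RSV-B neutralizing antibody titers from cord blood (or blood drawn from infants within 3 days after birth) will be tabulated". These are "tabulated with different categories of time (in weeks) from vaccination to delivery", separately for births before 37 weeks and from 37 weeks on. No maternal value enters the table, and the week categories are not given. Scatter plots are optional.

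Elsewhere the SAP measures transfer as a ratio:

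- **Section 2, Table 1.** The primary endpoint for the transfer objective is "The ratio between cord blood* and maternal RSVPreF3 IgG-specific antibody concentrations".
- **Section 9.1.2.** "Placental transfer is defined as the ratio of RSVPreF3 IgG-specific antibody concentrations between cord blood" (or early infant blood) and the maternal delivery sample.
- **Section 5.2.1.** "Geometric mean of placental transfer will be tabulated with 95% CI by study group".
- **Section 8.** Immunogenicity subgroups by maternal age and by gestational age at birth "will include analysis of GMT(C) and GMR calculation at each time point and geometric mean of placental transfer".

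None of these places tabulates the ratio by interval.

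**The concern.** The stated question is about transfer, and the reported outcome is the infant's level at birth. The two differ because the infant's level also depends on how much antibody the mother has at delivery. A longer interval allows more time for transfer, but it may also allow the mother's level to fall from its post-vaccination peak. The two effects can then work against each other in the cord level.

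A flat row of cord geometric means could be read as showing that the interval has no influence on transfer. A falling row could be read as declining transfer when only the maternal level has dropped. The analysis was added in SAP Amendment 1 specifically to understand the effect of the interval on transfer, so it should be able to address that.

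**Working it through.** The SAP gives no figure on this point, so there is nothing of its own to reproduce.

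**Identity.** From the definition in section 9.1.2, for RSVPreF3 IgG:

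cord level = maternal level at delivery × cord-to-maternal ratio.

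**Does another analysis fill the gap?**

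- The infant model in section 5.2.2.3 has antibody level as outcome and adjusts for the maternal pre-vaccination level, not the delivery level. Its interval term is commented out, with inclusion left optional.
- The maternal model in the same section does include the interval, but it describes the maternal level alone.
- The maternal-versus-infant plots in section 5.2.1 are by study group.
- Gestational age at birth is not the interval. Vaccination is allowed from 28 0/7 to 33 6/7 weeks, a span of 5 weeks 6 days (41 days). Births at the same gestational age can therefore differ by up to 41 days in interval.

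**Illustration 1: births at 28 and 70 days.** The 28 days is the per-protocol minimum of 4 weeks for infants (Table 6, code 3100). The 70 days corresponds to vaccination at 28 0/7 and birth at 38 0/7 weeks. Assumed, not from the SAP: maternal half-life h of 45, 60 or 90 days, and a ratio rising from 0.8 to 1.3, a factor of 1.3/0.8 = 1.625.

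Maternal factor = 2^(−(70−28)/h). Cord factor = 1.625 × maternal factor.

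| h (days) | Maternal factor | Cord factor |
|---|---|---|
| 45 | 0.524 | 0.85 |
| 60 | 0.616 | 1.00 |
| 90 | 0.724 | 1.18 |

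The same assumed 63% rise in the ratio appears as a 15% fall, no change, or an 18% rise.

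**Illustration 2: how large a rise would be hidden.** Between 4 weeks and an assumed 12 weeks (56 days), the rise in the ratio that leaves cord levels flat is 2^(56/h):

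| h (days) | 30 | 60 | 90 | 120 | 180 |
|---|---|---|---|---|---|
| Rise in ratio | 3.65 | 1.91 | 1.54 | 1.38 | 1.24 |

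**Illustration 3: what the table would show.** Compare 8–12 with 4–8 weeks, assuming intervals spread evenly and log-linear change. The category mid-points are 28 days apart, half of the 56-day span. The maternal factor is 2^(−28/h), which is 0.724 at h = 60. The ratio factor is the square root of the 4-to-12-week rise.

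| Scenario | Ratio, 8–12 vs 4–8 weeks | Cord, 8–12 vs 4–8 weeks |
|---|---|---|
| No change in ratio or maternal level | 1.00 | 1.00 |
| h = 60, ratio up 1.91-fold | √1.91 = 1.38 | 0.724 × 1.382 = 1.00 |
| h = 60, ratio constant | 1.00 | 0.72 |
| h = 60, ratio up 1.5-fold | √1.5 = 1.22 | 0.724 × 1.225 = 0.89 |

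The first two rows give the same entry in the planned table although the ratio behaves differently. In the last row the cord level and the ratio move in opposite directions.

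**The case against.** **Transfer may mean the amount delivered.** Section 9.1.2 defines placental transfer for RSVPreF3 IgG only, while section 5.2.2.1 speaks of antibody transfer for three assays. Section 5.2.2.4 also says that maternal infection may raise maternal antibody and so lead to more transfer to the infant, which is the amount sense. Under that sense cord levels are the right outcome. This stands as an ambiguity, so it goes too far to infer that the SAP plainly contradicts its own definition. The transfer objective in Table 1 is nevertheless tied to the ratio, and a reader will look for it.

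**The ratio is not a clean measure either.** Its denominator is the maternal level at delivery. In the 60-day case of Illustration 1 the infant's level is unchanged, the maternal level falls to 0.62, and the ratio rises by 1/0.616, about 1.62. The whole rise equals the fall in the denominator. This stands: one might infer that a ratio table recovers the transfer effect, but the identity cannot show that. The maternal level therefore has to be displayed beside it.

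**Related material exists.** The SAP includes the maternal model with interval, the individual plots and the ratio by gestational age at birth. Section 5.2.2.3 says that gestational age at birth, given gestational age at vaccination, carries similar information to the interval, and section 8 allows further subgroup analyses. These soften the point without supplying the ratio by interval.

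**Placebo.** The interval sentence does not repeat a split by study group, so a reader might infer that placebo recipients are pooled. Section 5.2.1 already sets the cord-blood analyses by study group, and table layouts are in a separate document, so that inference is not supported.

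**Conclusion.** The point holds as a mismatch between the stated purpose and the outcome of one descriptive analysis. On its own, the planned cord-level table cannot distinguish a change in transfer from a change in maternal level, and no specified table gives the ratio by interval.

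The size is unknown. The half-lives, the ratio values, the 12-week limit and the even spread of intervals are all assumptions, and the SAP quantifies neither maternal waning nor transfer over time. The illustrations show that cancellation or a reversed sign is possible, not that either will occur.

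A reader might also take the interval for the trial's main design lever. The SAP does not support this: vaccine group is what is randomised, gestational age at vaccination is one of three minimisation factors, and the interval is observed after randomisation. Section 6 makes all comparative analyses descriptive, so no error rate or sample size is affected. The cord-level table remains a sound description of what the infant has at birth.

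**What to change.** In section 5.2.2.1:

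1. Add the geometric mean RSVPreF3 IgG cord-to-maternal ratio at delivery, as defined in section 9.1.2, with 95% CI by interval category and study group.
2. Show the maternal delivery GMC by the same categories, so that a ratio rising only because its denominator falls is visible.
3. Keep the cord GMT/GMC table and label it as infant antibody level at birth.

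Ratios for RSV-A and RSV-B titres are optional and would need their own definition, because section 9.1.2 covers IgG only.

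The cost is SAP wording and one or two extra descriptive tables. The maternal and cord (or early infant) samples are already planned. Pairs without a maternal delivery sample drop out of the ratio table.
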